7.5.3.2. Serious Adverse Events

Each AE will be assessed to determine whether it meets seriousness criteria ([Section 7.5.1.2](#)). If the AE is considered serious the Investigator should report this event to the Sponsor. The Investigator shall also promptly report an SAE with a fatal outcome to the research ethics committee (REC). Serious adverse events occurring from the time of signed informed consent to the follow-up visit or 7 days after the last dose of study medication (whichever occurs later) will be recorded in source and electronic data capture; ongoing SAEs after this time frame will be followed until the Investigator, Medical Monitor, and Sponsor agree that the SAE is satisfactorily resolved, or stably unresolved.

Serious adverse events considered by the Investigator to be related to study medication, regardless of the time of onset after treatment, should be reported. All information about SAEs will be collected and reported via the SAE form and sent by email message (contact information

will be contained in the Investigator site file). The Investigator should send the initial report within 24 hours of becoming aware of the SAE.

At a minimum, the initial report should include the following information:

- Event
- Seriousness criteria
- Protocol number
- Subject number, initials, and age
- Study medication
- Reporter name and contact information
- Relationship assessment

In the case of a “minimum report” (one that solely comprises the information bulleted above), a more detailed follow-up report should be sent as soon as more information becomes available but no later than 3 calendar days after the date of the initial report.

Each SAE should be followed up until resolution or stabilisation and for reported deaths, the Investigator should supply Sponsor and the REC with any additional requested information (e.g., autopsy reports and terminal medical reports), if available. The original SAE form should be kept at the study site. The Investigator will be responsible for determining and in turn, reporting SAEs to the Sponsor.

7.5.4. Conditions That Should Not be Reported as SAEs

Any condition assessed by the Investigator as serious shall be recorded and reported to the Sponsor as an SAE.

7.5.5. Adverse Events Exemption

Not applicable. All AEs will be recorded in the eCRF by the Investigator and reported as described in this Protocol.

7.5.6. Prompt Reporting of Serious Adverse Events

Any SAE, occurring in a subject receiving treatment or if the Investigator becomes aware of any SAE post-treatment during the follow-up visit, should be reported by the Investigator via email to the Dompé Pharmacovigilance Department, Medical Monitor and EUDRAC Ltd within 24 hours even if the SAE does not appear to be medication-related.

The Investigator shall email a copy of the SAE form, in addition to other related information. Additionally, it may be necessary for the Medical Monitor or Sponsor to directly communicate with the Investigator if additional information is required.

All additional follow-up evaluations should be reported to the Sponsor. Such data should be emailed to the Dompé Pharmacovigilance Department, Medical Monitor and EUDRAC Ltd within 24 hours.

In line with CT3 Detailed Guidance and ICH E2A provisions, although the Investigator does not usually need to actively monitor subjects for AEs once the trial has ended, if the Investigator becomes aware of an SAE occurring in a subject after that subject has ended his participation

in the study (whether study completion or withdrawal), the SAE should be reported by the Investigator to the Dompé Pharmacovigilance Department. Such “post-study cases” should be regarded for expedited reporting purposes as though they were study reports. Therefore, a causality assessment and determination of expectedness are needed for a decision on whether or not expedited reporting is required.

A list of expected serious adverse reactions reported in patients treated with ketoprofen or gabapentin as single substances are provided in the IB.

7.5.7. Regulatory Reporting of Suspected Unexpected Serious Adverse Reactions (SUSARs)

During the course of the clinical trial, the Sponsor shall report any SUSAR to the concerned REC and regulatory authority, as soon as possible and in no event later than:

1. 7 calendar days after becoming aware of the information if the event is fatal or life threatening; to be followed by any relevant information within 8 calendar days.
2. 15 calendar days after becoming aware of the information if the event is neither fatal nor life threatening.

The Sponsor will be responsible for completing the safety report and for notifying the relevant authorities of any SAE as outlined in the ICH Guidelines and per local regulatory requirements.

Treatment will be unblinded by the Sponsor’s Pharmacovigilance Department prior to regulatory submission of a SUSAR to regulatory authorities and the REC, and only cases referred to active treatment will be considered suitable for expedition for regulatory reporting, in line with law requirements.

Follow up information shall be reported within the same timeframes.

If the results of an investigation show that an adverse drug reaction, not initially determined to be reportable, is reclassified as reportable, the Sponsor shall report such reaction in a written safety report as soon as possible, but in no event later than 7 or 15 calendar days (whichever is applicable) after the determination is made.

In addition, each Investigator will receive appropriate periodical safety updates as per local requirements and regulations.

The Sponsor shall be responsible to prepare and submit annual safety reports (Development Safety Update Report) to relevant regulatory authorities.

7.5.8. Special Considerations

7.5.8.1. Pregnancy of Female Partner of Male Subject

If the female partner of a male subjects becomes pregnant between dosing and 3 months after dosing, the Investigator should report pregnancy within 24 hours after learning of the pregnancy. The Investigator should contact the designated individual(s) following the SAE notification process and record information related to the pregnancy on the designated pregnancy form provided by Dompé or its designee. Early discontinuation visit assessments are required as soon as possible after learning of the pregnancy. The Investigator is also responsible for following any pregnancy following admission until delivery or termination if possible. These findings should be reported on the pregnancy form and forwarded to the designated individual(s). The event meets the SAE criterion only if it results in a spontaneous

abortion, congenital anomaly, or reports of suspected adverse reactions in the neonate that are classified as serious.

7.5.8.2. Overdose (if Appropriate)

Cases of overdose (accidental or intentional) which may or may not result in serious adverse reactions are to be reported to the Sponsor Pharmacovigilance Department and the Medical Expert following the same procedure for SAE, within 24 hours from the Investigator's knowledge of its occurrence. This includes reports related to drug intake through different routes (e.g., ingestion) or with suicidal intentions and consequent drug overdose.

In this study, an overdose is defined as the administration of a double dose or more, on any given treatment day.

The Investigator shall provide, in the SAE form, information about symptoms, corrective treatment and outcome of overdose. The Medical Expert should be contacted to discuss corrective treatment, if necessary.

7.6. Other Assessments

Assessments to be performed at Screening only and Day -1 only are detailed in the Schedule of Assessments ([Appendix 1](#) and [Appendix 2](#)).

8. PHARMACOKINETIC ASSESSMENTS

8.1. Pharmacokinetic Sampling

Baseline PK blood samples will be collected within 15 minutes predose on Day 1.

Blood samples for determination of plasma concentrations of ketoprofen and gabapentin when administered alone or in combination will be taken at the timepoints stated in [Appendix 1](#) and [Appendix 2](#).

The actual times of collection will be recorded.

Plasma concentration-time data will be analysed by noncompartmental methods. Nominal times may be used for interim decisions, however actual sampling times will be used for final calculations.

8.2. Storage and Analysis of Clinical Samples

Approximate sampling volumes are provided in [Appendix 3](#). Samples will be collected, labelled, stored, and shipped on dry ice as detailed in the Sample Handling Sheets.

Pharmacokinetic blood samples will be collected in polypropylene tubes containing Li-Heparin as anticoagulant, and they will be centrifuged at 4° C for 10 minutes at 2500 g to obtain plasma. Each plasma sample will be immediately divided into two aliquots and stored frozen at -20° C until shipment to the analytical laboratory. The samples will be analysed to quantify ketoprofen and gabapentin using a validated analytical method. The analysis will be performed at Dompé analytical laboratories in L'Aquila (Italy).

Further details will be provided in a standalone document.

9. PHARMACODYNAMIC ASSESSMENTS

9.1. Evaluation of Response to ID Capsaicin

The response to ID injection of capsaicin will be assessed in 6 ways; subjective rating of pain, area and pain score of hyperalgesia, area and pain score of brush-evoked allodynia and AF. Measurements will be taken prior to (within 15 minutes) and at the 15-, 30-, 60-, 90- and 120-minutes time points post injection. Prior to each injection, 4 intersecting lines forming 45-degree angles will be drawn on the skin using a fine-tipped skin marker for assessment of areas of hyperalgesia and allodynia. The 4 lines will intersect at the injection site and will be marked in 1cm graduations starting from the intersection.

9.2. Measurement of Pain

Pain will be measured on a visual analogue scale (VAS) consisting of a 100 mm line, with 0 representing “no pain” and 100 “worst pain imaginable.” Subjects will be asked to mark the VAS using a single vertical stroke at the point they consider to appropriately reflect their level of pain from the injection of capsaicin (not general pain). A new VAS will be provided for each time-point and subjects will not be allowed to see their previous VAS responses. The VAS will be scored by measuring from the left-hand end of the scale to the point where the subject has marked the line, and the distance in mm recorded.

9.3. Area and Pain Score of Hyperalgesia

The area of mechanical hyperalgesia will be assessed using a standard 24 g von Frey hair. The von Frey hair will be applied at 1-second intervals along each of the 4 lines intersecting at the injection site drawn onto the skin before the injection. Stimulation will begin distal from the injection site and will advance in 1cm increments toward the injection site until a pain response is elicited. Subjects will be asked to report when the von Frey hair first begins to cause any pain sensation or discomfort and the distance of that point from the injection site in centimetres for each line at each time-point will be recorded. The area of hyperalgesia will then be calculated and recorded in the CRF. Pain in response to von Frey stimulation of the hyperalgesic area will be recorded using an 11-point numeric rating scale (NRS) ranging from 0 (“no pain”) to 10 (“worst possible pain”). The pain score will reflect the maximum pain experienced during the assessment.

9.4. Area and Pain Score of Allodynia

The area of allodynia will be assessed by sweeping a standard paintbrush at 1-second intervals across each of the 4 lines intersecting at the injection site drawn onto the skin before the injection. Stimulation will begin distal from the injection site and will advance in 1 cm increments toward the injection site until a pain response is elicited. Subjects will be asked to indicate when the brush first begins to cause any pain or discomfort and the distance of that point from the injection site in centimetres for each line at each time-point will be recorded. The area of allodynia will then be calculated and recorded in the CRF. Pain in response to brush stimulation of the allodynic area will be recorded using an 11-point NRS ranging from 0 (“no pain”) to 10 (“worst possible pain”). The pain score will reflect the maximum pain experienced during the assessment.

9.5. Area of Flare

The AF will be determined by tracing the outline of visible skin reddening on to a sheet of acetate placed on the skin using a fine-tipped, permanent marker. The area will subsequently be measured using planimetry and the results recorded in the CRF.

10. STATISTICS AND DATA ANALYSIS

10.1. Randomisation and Subject Allocation

Randomisation schemes will be produced by MAC Clinical Research. Separate randomisation schemes will be produced for each of study Part A and study Part B. After informed consent is obtained, subjects will be allocated to a unique screening number.

A simple randomisation scheme will be performed for study Part A, while a blocked randomisation scheme will be used for study Part B. The block size for Part B will be 16, giving 8 blocks in total.

Only subjects who comply with all the inclusion criteria, and none of the exclusion criteria, will be randomised onto the study. The randomisation number will have 5 digital numbers, with the first being the study part (1 for Part A, 2 for Part B), the second being whether a subject is a replacement (0 = original; 1 = replacement), and the last 3 being the subject number; for example, 10011 means the 11th subject originally randomised for Part A, whereas 11011 is the replacement of 10011. All screened subjects should be identifiable throughout the study.

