Subject disposition will include a summary of the number and percentage of patients entered, enrolled, and treated as well as number and percentage of patients completing the study, or discontinuing. A summary of all protocol deviations will be provided.

Demographic and baseline characteristics, medical history, concomitant medication and treatment compliance will be summarised for all subjects by treatment.

AEs will be presented in terms of the number of AEs and incidence. Standard laboratory evaluations, vital signs, physical examinations, and 12-lead ECG parameters will be summarised by treatment at each available time point.

For Part A, PK parameters estimates will be calculated by noncompartmental methods. Pharmacokinetic data will be listed for each subject, along with summary statistics. A comparison of the main PK parameters obtained (C_{max} , AUCs, t_{max} and $t_{1/2}$) after KLS-GABA and ketoprofen administration will be presented. For Part B a PK/PD correlation will be implemented for all administered doses.

In Part B, the response to ID injection of capsaicin will be assessed in 6 ways (subjective rating of pain, area and pain score of hyperalgesia, area and pain score of brush-evoked allodynia and area of flare) and summarised using descriptive statistics.

Mixed Model Repeated Measures (MMRM) will be fit to data for each PD parameter using two groups of models. Group 1 will assess longitudinal changes in Scores / Area against baseline. Group 2 will assess differences in Scores / Area between treatments for each timepoint.

LIST OF ABBREVIATIONS

Abbreviation	Definition
ADME	absorption, distribution, metabolism and excretion
AE	adverse event
AF	area of flare
ALP	alkaline phosphatase
ALT	alanine aminotransferase
API	active pharmaceutical ingredient
AST	aspartate aminotransferase
AUC _{0-12h}	area under the plasma concentration-time curve from zero to 12 hours postdose
AUC _{0-24h}	area under the plasma concentration-time curve from zero to 24 hours postdose
AUC _{0-36h}	area under the plasma concentration-time curve from zero to 36 hours postdose
AUC _{0-48h}	area under the plasma concentration-time curve from zero to 48 hours postdose
AUC _{0-t}	area under the plasma concentration-time curve from zero to the last quantifiable concentration
AUC _{0-∞}	area under the plasma concentration-time curve from zero to infinity
BMI	body mass index
BP	blood pressure
CI	confidence interval
C _{max}	maximum plasma concentration

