3.3. Rationale for Study Design

This study is designed to evaluate the PK profile, safety, and tolerability of single oral doses of KLS-GABA compared to KLS alone in healthy male subjects (Part A), in addition to investigating the safety, tolerability, PK and PD effects of three single oral dose levels of KLS-GABA compared to three single oral dose levels of KLS alone, 300 mg gabapentin alone and placebo in the ID capsaicin model in healthy male subjects (Part B).

A crossover design will be utilised in Part A to permit a within-subject comparative assessment of the safety and PK of KLS-GABA compared to KLS alone in healthy male subjects. A minimum washout period of 7 days has been selected based on the $t_{1/2}$ of KLS and gabapentin, and therefore should be sufficient to ensure clearance of the drug.

Placebo is included in Part B of the study to permit comparative assessment of the safety and tolerability of KLS alone, KLS-GABA, and gabapentin alone, and to evaluate the balance of benefit and risk of KLS-GABA.

Intradermal injection of capsaicin has been widely used as a challenge agent to induce symptoms of neuropathic pain such as hyperalgesia and allodynia for periods of up to 8 hours post administration. In these challenge studies, capsaicin injection has been shown to be safe, well-tolerated and does not produce any lasting damage to the subjects injected. The use of ID capsaicin provides a safe and scientifically meaningful model to investigate the potential efficacy of drugs for neuropathic pain and other chronic pain conditions.¹⁴

This study includes standard assessments to evaluate safety and tolerability, including vital signs, physical examinations, 12-lead ECGs, clinical laboratory evaluations and AE collection.

Healthy male subjects have been selected for this study to mitigate any confounding effects of disease state and concomitant medications. Subjects with a skin type compatible with capsaicin measurements have been chosen, and subjects who can tolerate capsaicin injections, have been chosen to participate in Part B to allow collection of pain measurements.

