6.5. Subject Withdrawal Criteria

For all subjects withdrawn from the study, discontinuation procedures as described in [Appendix 1](#) and [Appendix 2](#) should be conducted prior to discharge in the study. In Part B, subjects will be replaced should they vomit after receiving their dose of IMP, or if they do not receive the ID capsaicin.

Reasons for withdrawal or discontinuation at any time during the study may include any of the following reasons:

- Adverse event: Clinical or para-clinical events occurred that, in the medical judgement of the Investigator for the best interest of the subjects, are grounds for discontinuation. This includes serious and non-serious AEs regardless of relation to the study medication.
- Withdrawal of consent: The subject desired to withdraw from further participation in the study in the absence of an Investigator determined medical need to withdraw. If the subject gave a reason for withdrawing it should be recorded in the eCRF.
- Investigator decision.
- Lost to follow-up: The subject stopped coming for visits and study personnel were unable to contact the subject.
- The subject tests positive for SARS-CoV-2 at any point during the study.
- Other: The subject was discontinued for a reason other than those listed above, such as termination of the study by the Sponsor. The reason(s) should be recorded in the eCRF.

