10.5.3. Pharmacokinetic Statistical Analysis

KLS, KLS-GABA and gabapentin concentrations and parameters will be summarised using all subjects in the PK Set. Full details of the PK analysis will be included in the PK Analysis Plan.

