4.3. Treatment groups

For summary statistics, subjects will be presented in different ways, as applicable:

- for Part A:
 - by planned treatment sequence of randomized subjects ("[KLS 80 mg - GABA 34 mg] – KLS 80 mg" and "KLS 80 mg – [KLS 80 mg - GABA 34 mg]"). This presentation will be used optionally for descriptive outputs (disposition, demographics, etc.), but generally will not be used for analysis of endpoints.
 - by actual treatment of subjects in each treatment period ("KLS 80 mg - GABA 34 mg" and "KLS 80 mg"). This presentation will be used for analysis of endpoints, and optionally for descriptive outputs (disposition, demographics, etc.).
- for Part B:
 - by planned treatment of subjects ("KLS 40 mg", "KLS 80 mg", "KLS 160 mg", "KLS 40 mg - GABA 17 mg", "KLS 80 mg - GABA 34 mg", "KLS 160 mg – GABA 68 mg", "Gabapentin 300 mg", "Placebo"). This presentation will be used for descriptive outputs (disposition, demographics, etc.).
 - by actual treatment of subjects ("KLS 40 mg", "KLS 80 mg", "KLS 160 mg", "KLS 40 mg - GABA 17 mg", "KLS 80 mg - GABA 34 mg", "KLS 160 mg – GABA 68 mg", "Gabapentin 300 mg", "Placebo"). This presentation will be used for analysis of safety, efficacy and PK endpoints.

Statistical Analysis Plan

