6.7. Pharmacokinetic Analysis

The PK analysis is outside the scope of this analysis plan. That analysis will be described in a separate document.

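### Part A, a 12-subject two-sequence crossover, uses simple rather than blocked randomisation; under independent 1:1 assignment the split is 8:4 or worse with 39% probability, an avoidable loss

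*Protocol*

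**What the plan says.** Protocol Section 10.1 reads: "A simple randomisation scheme will be performed for study Part A, while a blocked randomisation scheme will be used for study Part B". It then gives a block size of 16 and 8 blocks for Part B. For Part A it gives no allocation ratio, list method or balance constraint. The same section illustrates the numbering with a Part A case, in which "11011 is the replacement of 10011", but does not say which sequence the replacement follows. Replacement conditions appear in Section 6.5 for Part B only: "In Part B, subjects will be replaced should they vomit after receiving their dose of IMP", or if they do not receive the capsaicin injection.

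Part A plans 12 subjects in two periods (Protocol Sections 3.1 and 10.2). SAP Section 4.3 names two sequences and allows presentation "by planned treatment sequence of randomized subjects", but endpoints are to be presented by actual treatment in each period. Protocol Section 3.3 gives the reason for the design: "A crossover design will be utilised in Part A to permit a within-subject comparative assessment". The Synopsis promises "A comparison of the main PK parameters obtained" after the two treatments.

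The model for that comparison is in neither document. Protocol Section 10.5.3 says "Full details of the PK analysis will be included in the PK Analysis Plan", and SAP Section 6.7 says "The PK analysis is outside the scope of this analysis plan". Neither states a period term or rules one out.

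**The concern.** Section 10.1 sets simple against blocked in one sentence, so the natural reading is that nothing constrains the Part A split. Complete randomisation of 12 subjects to two sequences often leaves them unequal. In a two-period crossover the split determines either how precisely the treatment effect is separated from the period effect, or how much of the period effect leaks into it. Which of the two applies depends on whether the analysis adjusts for period. They are alternatives and do not add up.

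The comparison affected is Part A's primary objective. There is no sample size calculation (Protocol Section 10.2) and no hypothesis testing (SAP Section 3), so the result rests on the estimates and their precision. The protocol blocks Part B, with 16 subjects per arm, but not Part A, with 12 subjects in all. No effect on the timing of the Part B capsaicin injection is claimed.

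**Working it through.** The documents give no probability, power or precision figure for Part A, so there is none to reproduce.

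**Inputs from the documents.** 12 subjects; two sequences; two periods; simple randomisation.

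**Assumptions.** Each subject is assigned independently with probability 0.5 per sequence. For illustration only, within-subject CV is 15–30% and the period effect 5–20%; the documents give neither.

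**Formulas**, with n1 and n2 subjects per sequence and n1 + n2 = 12:

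- Probability of an unequal split n1:n2 = 2·C(12, n1)/4096; for 6:6 it is C(12, 6)/4096.
- Period-adjusted analysis: the variance of the log-scale treatment difference is sw²·0.5·(1/n1 + 1/n2). Relative to 6:6 this is a factor of 36/(n1·n2). The equivalent number of balanced subjects is 4·n1·n2/12.
- Upper 90% limit, as a percentage above the estimated ratio: exp[t(0.95, 10 df)·sw·√(0.5·(1/n1 + 1/n2))] − 1, with sw = √ln(1 + CV²).
- Unadjusted analysis: the share of the log-scale period effect entering the treatment difference is |n1 − n2|/12. The shift in the ratio is exp[share·ln(1 + period effect)] − 1.

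| Split | Probability | Variance factor (adjusted) | Equivalent balanced subjects | Upper 90% limit above ratio, CV 15% / 30% (adjusted) | Share of period effect (unadjusted) | Shift in ratio, period effect 5% / 20% (unadjusted) |
|---|---|---|---|---|---|---|
| 6:6 | 924/4096 = 22.6% | 1.00 | 12.0 | 11.7% / 24.3% | 0 | 0 / 0 |
| 7:5 | 1584/4096 = 38.7% | 1.029 | 11.7 | 11.8% / 24.6% | 17% | 0.8% / 3.1% |
| 8:4 | 990/4096 = 24.2% | 1.125 | 10.7 | 12.4% / 25.9% | 33% | 1.6% / 6.3% |
| 9:3 | 440/4096 = 10.7% | 1.333 | 9.0 | 13.6% / 28.5% | 50% | 2.5% / 9.5% |
| 10:2 or worse | 158/4096 = 3.9% | 1.80 or more | 6.7 or fewer | – | 67% or more | – |

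8:4 or worse: (990 + 440 + 158)/4096 = 1588/4096 = 38.8%. 9:3 or worse: (440 + 158)/4096 = 598/4096 = 14.6%.

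The variance factor averages 1.116 over lists with both sequences represented. About a third of the excess (0.039 of 0.116) comes from splits of 10:2 or worse. The median factor is 1.03, because 61% of lists are 6:6 or 7:5.

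A simulation of 200,000 trials per split, with sw = 0.2 and a 10% period effect, agreed. The adjusted estimate had bias near 0. The unadjusted estimate had log-scale bias of 0.016, 0.032 and 0.048 at 7:5, 8:4 and 9:3.

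**The case against.** The strongest reply is that the harm depends on a PK plan that is not available here. A period term in that plan would remove the bias entirely. The documents also standardise conditions between periods: single doses, an overnight fast, residency to 48 hours and a washout of at least 7 days. They give no ground for expecting a large period effect. Every subject is due to receive both treatments, so by-treatment summaries keep 12 planned subjects each at any split. Gabapentin is measured only after KLS-GABA, so there is no gabapentin contrast to lose. The CVs, period effects and 90% limits above are illustrations; neither document plans a Part A confidence interval.

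This limits the weight of the point. The typical loss is small: at 8:4 the standard error rises 6% (√1.125 = 1.061). An unadjusted analysis with no period effect gains nothing from balance, because the variance of the mean within-subject difference is then the same at every split. A balanced design is therefore never worse, but not always better.

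Two further replies carry less weight. Simple might loosely mean a single list with 6 per sequence fixed, but that runs against the sentence's own contrast with blocked, and if it is meant the protocol should say so. The paired replacement numbers may suggest that the sequence is inherited, but they do not state it.

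**Conclusion.** The concern holds. As written, Part A has no protection against sequence imbalance. Under independent 1:1 assignment the split is 8:4 or worse with probability 38.8%, and 9:3 or worse with probability 14.6%. With a period-adjusted analysis, 9:3 leaves the precision of 9 balanced subjects out of 12. Without adjustment, it lets half of any period effect into the KLS-GABA versus KLS difference. The average cost is modest, a variance factor of about 1.12 if the analysis is adjusted.

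The probabilities rest on the ordinary meaning of simple randomisation. The variance factors and leakage shares follow from the split alone. The percentage limits and shifts also rest on the assumed CV and period effect. Which form the harm takes cannot be settled without the PK Analysis Plan, but 6:6 is at least as good under both and better unless the analysis is unadjusted and there is no period effect. The sponsor should make the change. The unstated sequence for replacements is a secondary gap.

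**What to change.** Change Protocol Section 10.1 so that Part A uses a blocked list over the two sequences with 6 subjects per sequence, for example one block of 12. Add that any Part A replacement takes the sequence of the subject replaced. State in the PK Analysis Plan that the KLS-GABA versus KLS comparison includes a period term, because blocking balances the subjects randomised but does not guarantee 6 evaluable per sequence. If the Part A list already exists, report the realised split and rely on the period term.

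The cost is two sentences in Section 10.1, one parameter in the randomisation program and one line in the PK Analysis Plan. Section 10.1 is protocol text, so the change goes through the amendment route in Section 13.2 and is best combined with any other pending amendment. Predictability is not a real drawback: Part A is double-blind, and under Section 5.5 the unblinded pharmacy and dosing staff already have access to the randomisation list.
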